
2.4 Rationale

Several studies show that upregulation of the PI3K pathway is associated with poorer prognosis in patients with nonmetastatic RCC. Our data show that RCC patients treated with anti-VEGF therapy who have upregulation of components of the PI3K pathway have shorter PFS. In an 80 patient CTEP sponsored study of patients who received sorafenib or sorafenib plus IFN, AKT S473 was the single strongest predictor for clinical outcome in a panel of clinical and tissue variables. Similarly, analysis of nephrectomy samples in patients who received presurgical bevacizumab showed that upregulation of AKT was associated with a shorter PFS and poorer overall survival. We hypothesize that blockade

of AKT in patients who are refractory to anti VEGF therapy will eliminate one of the key drivers of tumor growth and proangiogenic signaling, and will result in prolongation of PFS.

2.5 Correlative Studies Background

Tissue Microarrays (TMA) to assess PI3K pathway protein levels: We have extensive experience in the generation and analysis of TMA in patients with RCC. Our recently published CTEP sponsored randomized phase II study of sorafenib vs sorafenib plus IFN used this technique on 40 formalin fixed, paraffin embedded nephrectomy specimens from patients on the study. We hypothesize that (1) upregulated AKT in nephrectomy specimens, including T308 and especially S473, will predict for response to MK2206 and (2) patients with baseline upregulated S473 will not show short PFS after treatment with the TORC1 inhibitor everolimus.

We assume that patterns seen in primary tumors are reflective of those expressed in metastatic sites. This assumption is supported by evidence that the karyotype and transcriptome is relatively similar when primary and metastatic disease is compared, and by unpublished observations from our group that protein expression in primary and metastatic sites is the same.

Cytokines and Angiogenesis Factors (CAF) in RCC: Analysis of the circulating microenvironment will provide insight into baseline and induced biomarkers associated with response and resistance to AKT inhibition. We have analyzed CAF from patient on the CTEP sorafenib trial, and have demonstrated biologically plausible associations with several factors, including VEGF and osteopontin. A five factor signature permitted discrimination between patients who benefitted from sorafenib plus IFN versus patients who benefitted from sorafenib monotherapy (Clin Ca Res, submitted). The purpose of the current study is to generate a similar set of observations in patients receiving TORC1 or AKT blockade.

We hypothesize that baseline and induced levels of CAF will be predictive for a response signature that identifies individuals who benefit from AKT blockade. Comparison between patterns in patients who receive an AKT blocking agent versus those who receive a TORC1 blocking agent will provide valuable information on the endocrine effects of AKT versus TORC1 blockade. These patterns may provide mechanistic insight into downstream pathways differentially affected by these two agents.

Virtual Karyotyping as a Predictive Biomarker in RCC: RCC karyotypic changes have been associated with clinical outcome in primary RCC. Preliminary data suggest that a specific karyotypic profile is associated with response and resistance to antiangiogenic therapy (abstracts, manuscript in preparation). Evaluation of chromosomal regions to elucidate mechanisms behind the karyotypic observations is underway. The purpose of the current study is to confirm our observations in a cohort of patients previously treated with anti-VEGF therapy, and to determine whether karyotypic patterns are predictive for response or resistance in TORC1 or AKT blocking agents.

We hypothesize that (1) Patients who showed a short PFS on prior anti-VEGF therapy will have a distinct karyotype, (2) These patients will show benefit to AKT blocking agents, and (3) Further karyotypic discrimination will be possible between patients who benefit from AKT blockade versus mTOR blockade.

3. PATIENT SELECTION

3.1 Eligibility Criteria

- 3.1.1 Patients must have histologically or cytologically confirmed metastatic or unresectable RCC. All histologies are permitted. Patient should have undergone nephrectomy.
- 3.1.2 Patients must have measurable disease, defined as at least one lesion that can be accurately measured in at least one dimension (longest diameter to be recorded for non-nodal lesions and short axis for nodal lesions) as ≥ 20 mm with conventional techniques or as ≥ 10 mm with spiral CT scan. See [Section 11](#) for the evaluation of measurable disease.
- 3.1.3 Patients must have received, and progressed on an anti-VEGF therapy, including bevacizumab, sorafenib, sunitinib or pazopanib.
- 3.1.4 Because no dosing or adverse event data are currently available on the use of MK-2206 or everolimus in patients < 18 years of age, children are excluded from this study but will be eligible for future pediatric phase 2 trials.
- 3.1.5 ECOG performance status ≤ 1 .
- 3.1.6 Patients must have normal organ and marrow function as defined below:
- leukocytes $\geq 3,000/\text{mcL}$
 - absolute neutrophil count $\geq 1,500/\text{mcL}$
 - platelets $\geq 100,000/\text{mcL}$
 - total bilirubin within normal institutional limits
 - AST(SGOT)/ALT(SGPT) $\leq 2.5 \times$ institutional upper limit of normal
 - Serum creatinine $\leq 1.5 \times$ ULN
- 3.1.7 INR and PTT $\leq 1.5 \times$ ULN. Therapeutic anticoagulation with warfarin is allowed if target INR ≤ 3 on a stable dose of warfarin or on a stable dose of LMW heparin for > 2 weeks at time of randomization.

- 3.1.8 The effects of MK-2206 and/or everolimus on the developing human fetus at the recommended therapeutic dose are unknown. For this reason, women of childbearing potential and men must use two forms of contraception (hormonal or barrier method of birth control; abstinence) prior to study entry, for the duration of study participation and for 8 weeks after the last dose of study drug. Should a woman become pregnant or suspect she is pregnant while she or her partner is participating in this study, the patient should inform the treating physician immediately.
- 3.1.9 Ability to understand and the willingness to sign a written informed consent document.
- 3.1.10 Serum pregnancy test in female patients of childbearing potential must be negative within 24 hours of enrolling on this study.

3.2 Exclusion Criteria

- 3.2.1 Patients who received oral TKIs (sorafenib, sunitinib, or pazopanib) within 2 weeks prior to entering the study, radiotherapy, immunotherapy or chemotherapy within 4 weeks prior to entering the study, bevacizumab within 4 weeks prior to entering the study, or those who have not recovered from adverse events due to agents administered more than 4 weeks earlier (recovered to \leq Grade 1).
- 3.2.2 Patients may not be receiving any other investigational agents. Patients may not have received an mTOR inhibitor.
- 3.2.3 Patients with known brain metastases should be excluded from this clinical trial because of their poor prognosis and because they often develop progressive neurologic dysfunction that would confound the evaluation of neurologic and other adverse events.
- 3.2.4 History of allergic reactions attributed to compounds of similar chemical or biologic composition to MK-2206 or other agents used in the study.
- 3.2.5 Patients receiving any medications or substances that are strong inhibitors or inducers of CYP 450 3A4 are ineligible. Lists including medications and substances known or with the potential to interact with the CYP 450 3A4 isoenzymes are provided in [Appendix C](#).

- 3.2.6 Patient should have a Hemoglobin A1C value of < 8%. Preclinical studies demonstrated the potential of MK-2206 for induction of hyperglycemia in all preclinical species tested. Studies also demonstrate a risk of hyperglycemia, hyperlipidemia and hypertriglyceridemia associated with everolimus therapy. Patients with diabetes or in risk for hyperglycemia, hyperlipidemia and/or hypertriglyceridemia should not be excluded from trials with MK-2206 or everolimus, but the patient should be well controlled on oral agents (recent (i.e. within 3 months) HbA1C \leq 7.0) before the patient enters the trial.
- 3.2.7 Preclinical studies indicated transient changes in QTc interval during MK-2206 treatment. Prolongation of QTc interval is potentially a safety concern while on MK-2206 therapy. Cardiovascular: baseline QTcF > 450 msec (male) or QTcF > 470 msec (female) will exclude patients from entry on study. A list of medications that may cause QTc interval prolongation are listed in [Appendix D](#), and should be avoided by patients entering on trial.
- 3.2.8 Uncontrolled intercurrent illness including, but not limited to, ongoing or active infection, symptomatic congestive heart failure, unstable angina pectoris, cardiac arrhythmia, or psychiatric illness/social situations that would limit compliance with study requirements.
- 3.2.9 Pregnant women are excluded from this study because MK-2206 and/or everolimus are agents with the potential for teratogenic or abortifacient effects. Because there is an unknown but potential risk for adverse events in nursing infants secondary to treatment of the mother with MK-2206 and/or everolimus, breastfeeding should be discontinued if the mother is treated with MK-2206 or everolimus.
- 3.2.10 HIV-positive patients on combination antiretroviral therapy are ineligible because of the potential for pharmacokinetic interactions with MK-2206 or everolimus. In addition, these patients are at increased risk of lethal infections when treated with marrow-suppressive therapy.
- 3.2.11 Individuals who are diagnosed with an intercurrent cancer are excluded, with the exception of non-melanoma skin cancers, and other cancers where curative treatment was completed at least two years ago.

3.3 Inclusion of Women and Minorities

Both men and women of all races and ethnic groups are eligible for this trial.

| Accrual Targets | | | | |
|--------------------|------------|---|-------|-------|
| Ethnic Category | Sex/Gender | | | |
| | Females | | Males | Total |
| Hispanic or Latino | 2 | + | 12 | = 14 |

| | | | | | |
|---|-----------|---|-----------|---|-----------|
| Not Hispanic or Latino | 28 | + | 72 | = | 100 |
| Ethnic Category: Total of all subjects | 30 (A1) | + | 84 (B1) | = | 114 (C1) |
| Racial Category | | | | | |
| American Indian or Alaskan Native | 1 | + | 1 | = | 2 |
| Asian | 0 | + | 0 | = | 0 |
| Black or African American | 6 | + | 6 | = | 12 |
| Native Hawaiian or other Pacific Islander | 0 | + | 0 | = | 0 |
| White | 23 | + | 77 | = | 100 |
| Racial Category: Total of all subjects | 30 (A2) | + | 84 (B2) | = | 114 (C2) |
| | (A1 = A2) | | (B1 = B2) | | (C1 = C2) |

4. REGISTRATION PROCEDURES

4.1 General Guidelines

See [Appendix K](#): Multi-Center Study Management Plan

Following registration, patients should begin protocol treatment within 5 days. Issues that would cause treatment delays should be discussed with the Principal Investigator. If a patient does not receive protocol therapy following registration, the patient's registration on the study may be canceled. The Study Coordinator should be notified of cancellations as soon as possible.

Except in very unusual circumstances, each participating institution will order DCTD-supplied agents directly from CTEP. Agents may be ordered by a participating site only after the initial IRB approval for the site has been forwarded by the Coordinating Center to the CTEP PIO ([contact]) except for Group studies.

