4.2 Registration Process

Before an institution may begin participation in a M.D. Anderson protocol, all the required steps outlined in [Section 3.3 of Appendix K](#) concerning regulatory documents, must be fulfilled.

Prior to protocol enrollment and initiation of treatment, subjects must sign and date an Institutional Review Board (IRB) approved consent form. Patients at participating institutions should be registered with their institutional central registration first, following each institution's established policies. All patients must then be registered in the M.D. Anderson database, Clinical Oncology Research System (CORe) before beginning treatment. CORe is a clinical research information management system supporting clinical research trials at U.T. M.D. Anderson Cancer Center and collaborative sites across the nation.

At the time of registration, the registrant will be requested to verify the patient's eligibility in

CORE by answering a series of inclusion/exclusion protocol questions and the name of the registering physician. Once patient eligibility has been established, the patient will then be automatically registered and randomized to the appropriate treatment arm. Therapy may then be initiated per protocol guidelines.

Please see [Section 3.3 of Appendix K](#) for registration requirements and data collection guidelines.

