8.1.3 Agent Accountability

Agent Inventory Records – The investigator, or a responsible party designated by the investigator, must maintain a careful record of the inventory and disposition of all agents received from DCTD using the NCI Drug Accountability Record Form (DARF). (See the CTEP home page at <http://ctep.cancer.gov> for the Procedures for Drug Accountability and Storage and to obtain a copy of the DARF and Clinical Drug Request form.)

8.2 **Commercial Agent: Everolimus**

Refer to the FDA-approved product package insert for comprehensive information.

How Supplied: Everolimus is commercially available as 5 mg and 10 mg tablets in blisters of 28 tablets. Each carton contains 4 blister cards of 7 tablets each.

Storage: Store everolimus tablets at 25° C (77°F); excursions permitted between 15°–30°C (59°–86°F). Store in the original container, protect from light and moisture.

Stability: Everolimus tablets are stable, when stored as indicated, until the expiration date identified on the package label.

Route of Administration: Oral

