13. STATISTICAL CONSIDERATIONS

13.1 Study Design/Endpoints

This is an open-label, multi-center, randomized phase II study. Patients will be randomized using 2:1 ratio to receive either MK2206 or everolimus. The primary endpoint of the study is progression-free survival (PFS), where an event is defined as either disease progression or death. The anticipated median PFS is 4.9 months and 8.2 months for the everolimus and MK2206 arms, respectively. The secondary endpoints include safety, overall survival (OS), overall response rate (ORR) and time to failure (TTF). For the primary endpoint, one interim futility analysis will be performed when a total of 38 events have occurred. The O'Brien-Fleming stopping boundaries using Lan-DeMets spending function will be used for early rejection of H1 (futility boundaries). At the interim look, if the nominal critical point (Z-scale) is less than 0.051, we will terminate trial, reject H1, and conclude that MK2206 has no significant effect on improving PFS. Assuming that the alternative hypothesis holds and trial is continued to completion without interim analysis, 105 patients with 75 events provide 81% power to reject null hypothesis. Since this trial has one interim analysis, 105 patients with 75 events provide 80% power to reject null hypothesis. Please see the detail information for power calculation in [section 13.2](#) sample size / power calculation.

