13.2 Sample Size/ Power Calculation

Assuming that the median progression-free survival (PFS) is 4.9 months and 8.2 months for the everolimus and MK2206 arm, respectively and patients will be randomized with 2:1 ratio into the MK2206 arm and the everolimus arm, then with a total of 75 events (i.e., disease progression or death), we will have an 80% power to detect such a 67% increase in median PFS using one-sided log-rank test and at a 0.10 significance level. The total number of patients to be enrolled will be 105, with 35 on the everolimus arm and 70 on the MK2206 arm. The above calculation also assumes an accrual rate of 4 patients per month, thus it will take 26.3 months to accrue all 105 patients. The maximum study duration will be around 29 months, which include patients' accrual period and a follow-up period. East5 software was used for the sample size/power calculation.

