13.3 Stratification Factors

Patients will be stratified by the MSKCC criteria ([Appendix J](#)) and type of prior therapy before being randomized into the MK2206 arm and the everolimus arm using a ratio of 2:1. The stratified randomization will be conducted through the Clinical Trial Conduct (CTC) website (<https://biostatistics.mdanderson.org/ClinicalTrialConduct>) maintained by the Department of Biostatistics of the University of Texas, M. D. Anderson Cancer Center.

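### Section 4.1 allows a registration to be canceled for non-treatment after open-label randomization, and nothing keeps such patients in follow-up or in the PFS, OS and TTF analyses

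*Combined protocol and SAP*

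**What the plan says.** - **Protocol 4.1 (General Guidelines).** "Following registration, patients should begin protocol treatment within 5 days". If a patient "does not receive protocol therapy following registration, the patient's registration on the study may be canceled". Delays are to be discussed with the Principal Investigator and cancellations notified to the Study Coordinator. The section gives no reason code, time limit, follow-up duty or analysis consequence.
- **Protocol 4.2 (Registration Process).** "Once patient eligibility has been established, the patient will then be automatically registered and randomized to the appropriate treatment arm". Therapy may start only after that.
- **Section 13.1.** "This is an open-label, multi-center, randomized phase II study".
- **Section 13.3.** "The stratified randomization will be conducted through the Clinical Trial Conduct (CTC) website", which is a different system from the registration database in 4.2.
- **Section 13.4.** PFS, OS and TTF all run from the date of treatment, and the arms are compared by stratified log-rank test. No analysis set is named for these endpoints.
- **Section 11.1.6.** PFS runs from randomization.
- **Section 13.5.2.** Conclusions rest on all eligible patients, but those who took no study medication may be excepted from the main response-rate analysis.
- **Section 5.6.** Contact is every 3 months after removal from study, and record review is an accepted means. Canceled registrations are not mentioned.

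**The concern.** A registration canceled because treatment never started is canceled after allocation, when site and patient can know the arm. If the decision not to start depends on both the arm and the prognosis, the patients who remain are no longer the groups that randomization produced. The primary PFS comparison and OS would then carry a bias that could not be measured afterwards, because the plan does not require outcomes to be collected on canceled patients. The control arm has 35 patients and the test is one-sided at 0.10, so a handful of removals could matter.

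The date-of-treatment origin in 13.4 adds to the problem. Even if a canceled patient were followed, that patient would have no start date for PFS, OS or TTF.

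**Working it through.** **1. Does any section protect a randomized patient who never starts?**

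| Question | Where | Answer |
|---|---|---|
| Is the arm assigned before therapy? | 4.2 | Yes |
| Can the arm be known? | 13.1 | Yes, open-label |
| May the registration then be canceled? | 4.1 | Yes, at discretion |
| Is follow-up required after cancellation? | 4.1, 5.6 | Not stated |
| Is there a time origin without treatment? | 13.4 / 11.1.6 | No / yes, for PFS only |
| Must the untreated be in the analysis? | 13.4, 13.5.2 | Not stated for PFS, OS, TTF; may be left out for response |

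**2. The plan's own power.** Inputs from 13.1 and 13.2: medians 4.9 and 8.2 months, 75 events, 2:1 allocation, one-sided 0.10.

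- Hazard ratio under exponential PFS: 4.9/8.2 = 0.598.
- Schoenfeld power: Φ(√(75 × 1/3 × 2/3) × |ln 0.598| − 1.2816) = Φ(4.082 × 0.515 − 1.282) = Φ(0.82) = 0.794.

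This agrees with the stated 80% (81% without the interim look). Accrual of 105 patients over 26.25 months gives 76.5 expected events at 29 months, which also fits 13.2.

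**3. Loss of power if c everolimus patients are canceled and not replaced.** The values of c are assumptions.

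| c | Power at 29 months | Power if the trial waits for 75 events |
|---|---|---|
| 0 | 0.800 | 0.794 |
| 4 | 0.773 | 0.781 |
| 7 | 0.750 | 0.768 |

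The loss is modest: 0.800 − 0.773, about 3 points, for four patients. Bias is the larger risk.

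**4. Type I error when cancellation depends on prognosis.** Assumptions: no true effect; control hazard ln 2/4.9 per month, halved in a random third of patients; 70 against 35 patients; accrual of 4 per month; log-rank at the 75th event; critical value 1.2816; no interim look. With 6,000 trials per cell, the Monte Carlo standard error near 19% is √(0.19 × 0.81/6,000), about 0.5 point. Results are rounded because repeat runs differ by about a point.

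| Patients canceled | Unstratified test |
|---|---|
| None | about 10–11% |
| 2 better-prognosis everolimus | about 12–13% |
| 4 better-prognosis everolimus | about 15–16% |
| 6 better-prognosis everolimus | about 19% |
| 6 everolimus at random | about 11% |
| 6 poorer-prognosis everolimus | about 8% |
| 6 better-prognosis MK-2206 | about 8% |

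When the better-prognosis everolimus scenario is analyzed with a log-rank test stratified on that same prognostic group, the error stays at about 10–12% for 0 to 6 cancellations. The inflation disappears because the strata hold all of the information that drove the cancellations.

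**5. Leverage by arm.** One loss is 1/35 = 2.9% of the everolimus arm and 1/70 = 1.4% of the MK-2206 arm. Six losses are 6/35 = 17% of the everolimus arm, and about half of its expected 35/3 ≈ 12 better-prognosis patients.

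**The case against.** **The planned test is stratified.** Section 13.3 stratifies by MSKCC risk and type of prior therapy, and 13.4 uses a stratified test. If those factors explain who declines, little bias is left. This stands as a limit on size: 19% is the extreme in which the strata capture none of the relevant prognosis, and 10–12% is the extreme in which they capture all of it. Nothing shows where the trial would fall between them.

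**Six selective cancellations in one arm is a severe case.** These are consented patients expected to start within 5 days, with delays discussed with the Principal Investigator. That also stands. With two cancellations the unstratified figure is only 12–13%.

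**Stronger readings that the documents do not support:**

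- *Everolimus patients would be the ones to leave.* A reader might infer this because "Everolimus is commercially available as 5 mg and 10 mg tablets" (8.2) and section 2.1 reports its approval after sorafenib or sunitinib, while MK-2206 is supplied through NCI. The argument can be turned around: a patient allocated the unproven agent may decline it in order to take the approved one. Section 4.1 does not distinguish arms.
- *The bias would favor MK-2206.* The table in the working shows it can go either way.
- *Canceled patients get no scans, contact or outcome.* Section 4.1 does not say so. Section 5.6 follows patients after removal from study, and 13.5.2 wants every included patient assessed for response. Whether a canceled patient counts as removed or included is unclear. The defect is that silence, not a stated loss of data.
- *The accrual table's 114 against 105 in 13.2 shows planned replacement.* Nothing links the extra 9 to cancellations, so it is no support here.

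**Registration and randomization may be separate steps.** Section 13.3 puts randomization on another website. The two sections should be reconciled, but 4.2 still places randomization before therapy.

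**Conclusion.** The point holds. Sections 4.1, 4.2 and 13.1 together permit removal after the allocation is known, and no section secures follow-up or inclusion in the PFS, OS or TTF analysis. The treatment-date origin in 13.4 would exclude the untreated even if their registrations stood.

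The size cannot be derived from the documents, because no cancellation rate is given overall or by arm. Under the assumptions above, six selective cancellations put the nominal 10% error anywhere from about 8% to 19% unstratified, and near 10–12% if stratification captures the prognostic factor fully. Cancellations unrelated to prognosis leave it at baseline. The direction is unknown in advance. The change is worth making because the plan allows a bias that it could not later measure, and closing the gap takes a few lines.

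**What to change.** **Section 4.1.** Allow cancellation only before the allocation is released. A randomized patient who does not start treatment:

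- stays registered in the assigned arm and is not replaced;
- has the reason recorded, with numbers and reasons reported by arm;
- unless consent is withdrawn, is followed for progression from routine scans and for survival through the 3-monthly contact in 5.6, which should name these patients.

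**Section 13.4.** Analyze all randomized patients as assigned, and date PFS, OS and TTF from randomization. This brings PFS into line with 11.1.6. Without this change the one in 4.1 does not work, because an untreated patient would have no start date.

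**Sections 4.2 and 13.3.** State which system randomizes and when the result is released. Tying the 4.1 rule to that release makes it work whichever system is used.

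**Cost.** Record review or telephone follow-up for a few untreated patients, with no added study visits or scans. Including them dilutes a true treatment effect slightly. The design stays at 35 + 70 patients and 75 events, and no treatment rule changes.
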